**Table 1**

PERIOD	TIMING	PROCEDURES
ADP	10 am	Breath alcohol levels, AUQ, YCS, TLFB, SAFTEE, CADSS, Vitals Administer last doses of medications
	11 am	Approach Avoidance Task, Impulsivity tasks; Self report and Laboratory measures
	12 pm	Lunch and Smoke Break for smokers
	1 pm	Insertion of IV for blood alcohol draws
	2 pm	Start of baseline; AUQ, YCS, BAES, Vitals; Smoke break for smokers
	2:30 pm	AUQ, YCS, BAES, Vitals
	2:45pm	YCS
	2:50 pm	Alcohol cue exposure to preparation of priming drink (PD)
	2:59 pm	YCS
	3 pm	Priming dose period: Instruct participant to consume PD (0.03g/dl) in five minutes

	3:10 pm	Blood alcohol, AUQ, YCS, BAES
	3:20 pm	Blood alcohol, AUQ, YCS, Vitals
	3:30 pm	Blood alcohol, AUQ, YCS, BAES
	3:40 pm	Blood alcohol, AUQ, Vitals
	3:50 pm	Blood alcohol, AUQ, YCS, BAES
	4 pm First tray	1 st Self-administration (SA) period: Bring in first tray of 4 drinks (each designed to raise BAL by .015 g/dl) and drinking tab (\$12); Instruct participants on choice of drinks versus money.
	4:30 pm	AUQ, YCS, BAES
	5 pm Second tray	Blood alcohol, AUQ, BAES, Vitals @ 4:55 pm 2 nd SA period: Remove first tray and bring in second tray: Present participant with 4 drinks (each will raise BAL by .015 g/dl) and drinking tab (\$12); repeat instructions
	5:30 pm	AUQ, YCS, BAES
	6 pm Third tray	Blood alcohol, AUQ, BAES, Vitals @ 5:55 pm 2 nd SA period: Remove second tray and bring in third tray: Present participant with 4 drinks (each will raise BAL by .015 g/dl) and drinking tab (\$12); repeat instructions
	6:30 pm	AUQ, YCS, BAES
	7 pm	Blood alcohol, AUQ, BAES, YCS, Vitals
	7:30 pm	Dinner
	8 pm	Breath Alcohol, AUQ, YCS, BAES, Vitals
	9 pm	Breath Alcohol, AUQ, YCS, BAES, Vitals
	10 pm	Breath alcohol, AUQ, YCS, BAES, Vitals
Discharge	7 am	Breath alcohol, AUQ, YCS, Vitals, CADSS, BPRS

g. *End of alcohol self-administration period and overnight stay in HRU:* The alcohol administration portion of the study will end at 7:05 pm. Following this, breath alcohol levels and craving will be assessed every 30 minutes until the subject's breath alcohol level falls below 0.02. Participants will then be given dinner and will stay in the hospital overnight. This overnight stay will serve multiple purposes: 1) to ensure that subjects do not continue to drink following exposure to alcohol in this paradigm, 2) to ensure that they are safe and are not discharged while still intoxicated, and 3) to motivate subjects to drink during the session by ensuring that they do not have an opportunity to have access to more alcohol later that same day. The next morning participants will be assessed using craving and withdrawal measurements, they will be provided with breakfast, and they will then be discharged between 8 and 9 am.

#### Study Medication (Naltrexone/Memantine/NAC) Administration and Stabilization: 6-8 Days

All subjects will receive naltrexone treatment and be randomly assigned to receive either memantine 20 mg, NAC 2400 mg or placebo for seven days as outpatients. The randomization schedule will be generated by the Data Management and Biostatistics Component statisticians and provided to the pharmacist. They will take the final dose of 50 mg NTX + 20 mg MEM or 2400 mg NAC or placebo, when they will complete the alcohol self-administration paradigm described below. Doses of naltrexone and memantine will be tapered up as follows

GROUP	Day 1	Day 2	Day 3	Day 4	Day 5	Days 6-8 (up to 13)
Naltrexone	25 mg	50 mg	50 mg	50 mg	50 mg	50 mg
Memantine/ NAC/placebo	0/0/0 mg	0/0/0 mg	5/600/0 mg	10/1200/0 mg	20/1200/0 mg	20/2400/0 mg

Subjects will come to our clinic each day to take their medications at 10 am. During these appointments they will complete assessments. These procedures will 1) ensure compliance with medication administration, 2) monitor side effects during naltrexone and memantine/nacetylcysteine dose escalation, and 3) monitor tolerability of naltrexone, memantine, and NAC co-administration. ***During this period, subjects will be asked to continue normal drinking behavior similar to the procedures used in our preliminary studies.***

In the event that a subject cannot come to the clinic daily, other arrangements will be made, such as giving the participant more than one dose of their medication at a time and using a daily phone call as both a reminder to take the medication and as a means to monitor adverse events. We will allow this up until the final two doses of medication prior to the ADP. This arrangement will be determined by the investigator and her staff based on the participant's other obligations and compliance.

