The study will consist of five phases: 1) **Phase 1 (Screening):** We obtain informed consent and evaluate eligibility for the study using clinical assessments and physical exams, if eligible, participants will be scheduled for the rest of the study, 2) **Phase 2 (Baseline):** Participants will complete some memory and mood tasks, participate in the PIT task, and complete a baseline alcohol drinking paradigm (ADP), 3) **Phase 3 (Med 1):** The first 6-8day outpatient medication phase during which participants will come into our clinic every day to take the medication combination they have been assigned and participate in the second ADP on the last day of medication, (participants may be asked to take the medication for up to 13 days, based on scheduling for their overnight stay) Also, in the event that a medication appointment will be missed because the participant is unable to come to the clinic the following day, he/she will be given an extra dose of medication to take home for the next day. The participant will be called the next day as a reminder to take the medication and will also be asked about any adverse events. 5) **Phase 4 (Washout):** At least 6-8 day washout phase (length of washout based on hospital scheduling) and 6) **Phase 5 (Med 2):** Participants will be randomized to receive another medication combination for 6-8 days which will culminate in the third ADP (again, this is based on scheduling for the overnight at the hospital and can be extended to 13 days). In the event that a participant is unable to make it to one of the overnight visits, and needs to discontinue one of the medication periods early due to personal circumstances, we would like to have the option of restarting the medication. We do not believe that this will increase risk to participants since they would have already taken the medications during an earlier phase. It is essential that participants complete all parts of the study for us to be able to use the data to evaluate the effects of combining naltrexone and memantine on drinking behaviors.

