Alcohol is a reinforcing agent, which may cause changes in behavior including repetitive or excessive alcohol consumption. Because of this, the administration of alcohol to alcoholics in treatment could potentially impede the progress of their recovery. In addition, the administration of alcohol to sober alcoholics living in the community presents a possible risk of relapse. As a result, we will be recruiting **non**-abstinent **non**-treatment seeking alcoholics in keeping with the National Advisory Council on Alcohol Abuse and Alcoholism's (1989) recommended guidelines on ethyl alcohol administration. At completion of the study, we will make a serious and concerted effort to link the subject with treatment for their alcohol problems. This will be done by giving the subject objective feedback about the fact that their drinking exceeds standards for avoiding hazardous drinking, providing a brief one session motivational intervention for their drinking, and by arranging for alcohol treatment services if they are interested. In our previous and ongoing work, several participants quit drinking and many others reduced their drinking in the three months following this intervention (Sinha R, Krishnan-Sarin S, Farren C, O'Malley SS. Naturalistic follow-up of drinking behavior following participation in an alcohol administration study. *Journal of Substance Abuse Treatment* 1999; 17: 159-62).

5) Interactions of Memantine and Alcohol:

There are no known interactions of co-administering memantine and alcohol. In a study by Bisaga and Evans [40] in moderate drinkers, memantine by itself produced some increase in dissociative symptoms which were further slightly increased by alcohol. Since, in this study,

participants will be taking memantine on an outpatient basis, we will monitor via face-to-face daily contact for side effects from memantine.

6) Interactions of NAC and Alcohol:

There are no known interactions of co-administering NAC and alcohol. Since, in this study, participants will be taking NAC on an outpatient basis, we will monitor via face-to-face daily contact for side effects from NAC.

7) Interactions of Naltrexone and Alcohol:

There are no known risks to contraindicate the administration of alcohol to subjects on naltrexone. It has been shown that pharmacokinetics properties of naltrexone and ethanol are not altered on simultaneous administration of both agents.

8) Intravenous Access:

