Insertion of an intravenous catheter involves risk for hematoma at the site of the venous puncture. Very rarely, venous puncture can also result in a blood clot or infection.

9) Blood and Urine Collections:

Screening blood and urine collections are performed primarily as safeguards to subjects and should add no risks other than those normally associated with these procedures. Subjects will have approximately 40 cc of blood drawn at the intake appointment to determine liver and kidney functioning, 30 cc of blood for the genetics portion (see below) and during the fourth phase (self-administration) of the study we will draw approximately 30 cc of blood. Therefore, the total amount of blood drawn during the study (100 mls or approx. 3.4 oz) is well within the HIC guidelines of 450 cc within eight research weeks and the blood loss poses minimal risk in healthy subjects. We will advise subjects against donating blood for six weeks following study participation.

10) Rating Scales and Questionnaires:

These are all noninvasive and should add no risk. The major disadvantages are the time taken to complete them, and possible breach of confidentiality. Our past experience with these measures indicates that they are acceptable to subjects. Careful efforts aimed at maintaining confidentiality will be made.

11) Alcohol Withdrawal:

We will not ask participants to alter their drinking behavior during their participation in the study. However, there is always the possibility that some participants may reduce or stop drinking during the outpatient period while on the study medication. Therefore, we will inform that that some individuals who reduce or stop their drinking can experience alcohol withdrawal symptoms such as mild agitation, anxiety, restlessness, tremor, loss of appetite and difficulty sleeping or even more severe (but rare) symptoms like extreme restlessness, nervousness, disorientation, confusion, hallucinations (hearing and seeing things that are not there) and seizures, but these are extremely rare. We will monitor them daily during their visits to our clinic and will also inform them that if they experience worsening of withdrawal symptoms (CIWA > 8) we may have to hospitalize them and give them medications that are typically used to treat and manage withdrawal including benzodiazepines, such as chlordiazepoxide (librium), and other medications such as carbamazepine (tegretol).

12) Genetic Bloods:

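### The procedures allow home dosing on escalation days with a daily phone call, while the risk section states daily face-to-face monitoring without exception

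*Combined protocol and SAP*

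**What the plan says.** **Procedures.** Section V.3, Study Medication Administration and Stabilization, makes a daily 10 am clinic visit the default. One stated purpose of the visits is to watch for side effects while doses rise. Participants are asked to keep drinking as usual. For someone who cannot attend every day, the plan permits other arrangements, one example being "giving the participant more than one dose of their medication at a time and using a daily phone call as both a reminder". That call is also how adverse events are followed on such days. The timing limit is: "We will allow this up until the final two doses of medication prior to the ADP". On who decides, and on what grounds: "This arrangement will be determined by the investigator and her staff based on the participant's other obligations and compliance".

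The Phase 3 (Med 1) description earlier in Section V.3 is narrower. If a visit will be missed, "he/she will be given an extra dose of medication to take home for the next day", and staff telephone that day as a reminder and to ask about adverse events.

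**Risk sections.** Section IX.1, item 5 (memantine and alcohol): "participants will be taking memantine on an outpatient basis, we will monitor via face-to-face daily contact for side effects from memantine". Item 6 (NAC and alcohol): "participants will be taking NAC on an outpatient basis, we will monitor via face-to-face daily contact for side effects from NAC". Item 11 (alcohol withdrawal): "We will monitor them daily during their visits to our clinic". Section IX.2, item 1, also places side-effect monitoring for memantine at the daily medication visits. None of these four places mentions a telephone alternative.

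**The concern.** The risk sections describe one mode of monitoring and the procedures permit another. The difference can fall on the days when doses rise in people who are still drinking. The only timing limit on home dosing is tied to the drinking session, not to the dose steps, and the stated grounds for allowing it do not include how the current dose has been tolerated. Read literally, a participant could leave with the next, higher dose before anyone has seen the response to the present one.

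Two things are at stake. The first is whether readers of the risk sections get an accurate account of how participants are watched. The second is the tolerability data. Tolerability of the two combinations is the secondary aim (Section V.1), and the Power Analysis in Section V.4 names initial tolerability as a use of the pilot, with 10 completers per group. If some adverse events are collected in person and others by telephone, and the mode is not recorded, a difference between conditions is harder to interpret in groups that small.

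**Working it through.** The plan gives no figure to reproduce. The check sets the home-dosing window against the dose table.

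**Inputs**
- Dose steps (table in Study Medication Administration and Stabilization). Naltrexone goes from 25 to 50 mg on Day 2. Memantine goes to 5, 10 and 20 mg on Days 3, 4 and 5. NAC goes to 600 mg on Day 3, 1200 mg on Day 4 and 2400 mg on Day 6.
- Length of a medication period, L: 6 to 8 days, up to 13 (Section V.3, Research Plan).
- The drinking session falls on the last medication day (Phase 3 description). That day's dose is given at 10 am in the session (Table 1).
- Assumption: the Day 1 dose is taken in clinic, so the window opens on Day 2.

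**Two readings of the limit**
- Reading A: the final two doses are the session-day dose and the one the day before. The last possible home day is L − 2.
- Reading B: they are the doses on the two days before the session day. The last possible home day is L − 3.

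The number of eligible days is (last home day) − 2 + 1. For L = 8 under A, the last day is 8 − 2 = 6, and Days 2-6 make 5 days. Under B, the last day is 8 − 3 = 5, and Days 2-5 make 4 days.

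| L | Reading A: home days (number) | Steps inside | Reading B: home days (number) | Steps inside |
|---|---|---|---|---|
| 6 | 2-4 (3) | NTX 2; MEM 3, 4; NAC 3, 4 | 2-3 (2) | NTX 2; MEM 3; NAC 3 |
| 7 | 2-5 (4) | NTX 2; MEM 3, 4, 5; NAC 3, 4 | 2-4 (3) | NTX 2; MEM 3, 4; NAC 3, 4 |
| 8 | 2-6 (5) | NTX 2; MEM 3, 4, 5; NAC 3, 4, 6 | 2-5 (4) | NTX 2; MEM 3, 4, 5; NAC 3, 4 |
| 13 | 2-11 (10) | NTX 2; MEM 3, 4, 5; NAC 3, 4, 6 | 2-10 (9) | NTX 2; MEM 3, 4, 5; NAC 3, 4, 6 |

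(Entries under Steps inside are the days of dose increases that could be taken at home.)

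Every cell contains at least one step of each of the three drugs. The readings differ at the upper end. In an 8-day period the NAC step on Day 6 is inside the window under A and outside it under B. In a 13-day period every step after Day 1 is inside under both.

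**The texts side by side.** Items 5 and 6 of Section IX.1 cannot be met literally on a day when the contact is a telephone call. The Phase 3 description covers one missed visit and one extra dose. The medication procedures cover more than one dose at a time, with no stated number.

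**The case against.** The strongest reply is that this is a rule with an exception, and that both stand in the same application. Clinic dosing is the default. Home dosing arises only when someone cannot attend, is decided case by case, and takes compliance into account. Items 5 and 6 can be read as describing the default, and whoever read them also had the procedures. Daily contact continues by telephone and covers adverse events. Other protections remain, such as the medical and withdrawal-history exclusions (Section VII.3) and the emergency card for memantine (Section IX). The two home-dosing descriptions are also not strictly contradictory, because the Phase 3 text does not say that one extra dose is the maximum.

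Much of this stands. The exception is probably occasional, and monitoring changes mode without stopping. A reader might infer that the safeguard is removed altogether; the documents do not support that, because a daily call remains. But the reply does not settle the conflict. The risk items state no exception, and the exception has no cap on consecutive doses and no reference to dose steps, although escalation is a stated reason for the visits.

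It is also fair to say that the last two doses are protected, close to where the drinking outcome is measured. That helps the session outcomes. It does not address tolerability during escalation.

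**Conclusion.** The inconsistency is real and should be corrected. The procedures permit telephone monitoring where the risk sections describe face-to-face or clinic monitoring, on 2 or 3 days of a 6-day period, 4 or 5 of an 8-day period and 9 or 10 of a 13-day period. At least one step of each drug is covered in every case. These are permitted days, not expected ones, since the documents do not say how often home dosing will be used. The counts assume that Day 1 is in clinic and the session is on the last medication day. The upper end of the window depends on which doses are the final two, which the text leaves open.

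Stronger conclusions that a reader might draw are not supported:
- **Every step after Day 1 can be taken at home in an 8-day period.** This holds only under reading A.
- **Unobserved doses are counted as taken and dilute the treatment contrast.** The documents do not say how doses are counted, and the dosing form is not among them.
- **A CIWA at each visit is lost.** Item 11 of Section IX.1 refers to daily monitoring and a CIWA level, but the plan does not schedule the scale at every visit.
- **The consent form is wrong on this point.** Its text was not available for review.

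**What to change.** Reconcile the Phase 3 description and the medication procedures in Section V.3 with items 5, 6 and 11 of Section IX.1 and item 1 of Section IX.2, so that the monitoring described to readers of the risk sections matches what staff are permitted to do. The reconciled text should make clear which doses the final two are, whether consecutive home doses are limited, and how the arrangement relates to the escalation days. Which rule applies is a clinical decision for the investigators.

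Under any rule, record each dose as observed or unobserved, together with the mode of that day's adverse-event contact (clinic or telephone). Report both by treatment condition alongside the tolerability results, so that a reader can see whether adverse events were collected in the same way in each condition.

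The cost is protocol wording and one added item on the dosing record.

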#### Follow-up Appointments

Subjects will participate in a one-week follow-up appointment during which drinking over the past week will be determined using TLFB techniques and any remaining adverse events will be monitored. At this appointment a brief motivational intervention will be provided to encourage the subject to address their alcohol problem and an immediate referral to treatment will be made if subjects are interested. Even though the subjects participating in this study are not seeking treatment for their drinking, we feel that their participation in this project provides us with a “teaching moment” to address their drinking behavior. We have found that similar brief advice resulted in decreases in alcohol-drinking behavior and increased motivation to quit drinking (Sinha et al., 1997). As previously done, this intervention will be based on the principles of Miller’s Motivational Enhancement Therapy (MET) (Miller et al., 1992). We will provide subjects with personalized feedback regarding their physical exam and laboratory findings, and on the influence of drinking on their health. We will also review with them the potential benefits of quitting drinking. If interested, subjects will also be given the option of participating in one of our alcohol treatment studies. We will also provide them with the NIAAA brochure “Rethinking Drinking.”

Subjects will also participate in a one-month follow-up appointment during which information about their drinking since their prior appointment will be assessed using the Time-Line Follow-Back Interview. This interview provides us with another opportunity to provide subjects with additional information about treatment if they are interested. This data will also be used to evaluate the risks and benefits for subjects participating in this protocol (O’Malley et al., 2002; Anton et al., 2004).

#### Assessments

- Socio-demographic/General Information:** At intake, demographic data, medical history, and family psychiatric history will be assessed with interviews and self-report forms that provide data on age, race, socioeconomic status, marital status, educational and occupational levels, and significant medical history. These are adapted from previous diagnostic and clinical studies at this center.

b) SCID: The Structured Clinical Interview for DSM-IV (SCID) (First et al., 1996) will be used to determine psychiatric diagnoses. This interview assesses DSM-IV current and lifetime psychiatric diagnoses for anxiety, mood, psychotic, alcohol and substance use, somatoform, and eating disorders.

c) Psychiatric Family History by Interview, the FHAM: As a source of pedigree information, the psychiatric status (including substance abuse/dependence, mood disorder, ASPD, etc.) of all first- and second-degree biological relatives will be obtained from each subject (including parents) using the family history method (FHAM-Family History Assessment Module) developed by COGA. DSM-IV criteria will be used to diagnose all biological family members. The FHAM is a reliable method for obtaining family history information and the specificity and sensitivity of the FHAM for the diagnosis of substance dependence is quite good (Rice et al., 1995). We will administer the FHAM in three steps. First, the structure of the family pedigree is drawn and reviewed with the informant. Next, psychiatric screening questions are asked about all relatives in the pedigree. Then, based on the responses to the screening questions, symptom checklists are completed for each first-degree relative, spouse, or other relative well known to the informant.

d) Time-Line Follow-Back Assessment Method: This interview procedure will be used to obtain quantity/frequency alcohol consumption data for each day during the 90-day period prior to the study, during the outpatient stabilization period, and during the three-month follow-up (Sobell and Sobell, 1992). Subjects are given a blank calendar covering the time interval to be re-constructed and are asked to reconstruct retrospectively their drinking behavior over that interval. The process is facilitated by establishing anchor points (e.g., holidays, anniversaries, major national events, etc.). It can be scored to provide the number of days on which various levels of consumption occurred. The time-line method has good test-retest reliability and good validity for verifiable events. It has been used in numerous studies to compare pre- to post-treatment drinking.

e) Craving Measures:

*Alcohol Urge Questionnaire (AUQ)* (Bohn et al., 1995): The AUQ is an 8 item questionnaire, derived from a larger 49 item "Questionnaire of Alcohol Urges," that assesses *desire for a drink, expectation of positive effect from drinking, and inability to avoid drinking if alcohol was available*. The AUQ is a reliable and valid scale for the measurement of self-reported alcohol urges, and scores have been shown to be strongly related to alcohol dependence severity (as measured by ADS scores) and to cognitive preoccupation with alcohol. Its brevity and time frame for ratings (i.e., right now) makes it suitable for administration during the alcohol drinking period.

*Yale Craving Scale (YCS)*: We have been collaborating with [name] to develop this craving measure based on psychophysiological scaling methods. In her work on individual differences in the ability to taste bitterness, [name] and colleagues (Marks et al., 1988) used magnitude-matching procedures (Stevens and Marks, 1980) in which participants matched the intensity of perceived bitterness to sounds. By doing so, the problem of differences in how labels (e.g., very strong) are applied was circumvented by making the comparison to a standard that is unrelated to taste. The resulting scale, Labeled Magnitude Scale (gLMS) (Bartoshuk, 2002), has been extended to measure hedonic ratings for foods, and we have adapted it for rating craving for tobacco and alcohol. It is not subject to the ceiling effects that often occur in craving research (Sayette et al., 2000). We have been collecting craving data using this scale in our ongoing projects and the findings from this scale have been found to parallel those obtained using the Alcohol Urge questionnaire. *A significant advantage of this scale is that following completion of baseline training to match perceived intensity of craving to the perceived brightness from the sun, each assessment timepoint only consists of a single visual analog scale of craving, making it very easy to administer.*

f) Clinical Institute Withdrawal Assessment for Alcohol-Revised (CIWA-Ar): This is a modified, shorter version of the Clinical Institute Withdrawal Scale for Alcohol which is equally efficient and reliable as the original scale without a significant loss in accuracy. The CIWA-Ar is a 10 item scale that contains alcohol withdrawal signs and symptoms that include nausea/vomiting, tremor, headache, anxiety, agitation, orientation, sweating, and auditory, visual, and tactile disturbances. This tool often guides the clinical management of alcohol (Sullivan et al., 1991) withdrawal (for a review, see Saitz and O'Malley, 1997) and is used extensively in research on alcohol withdrawal (Sellers et al., 1991; Saitz et al., 1994).

g) Psychiatric and mood symptoms: We will assess changes in these symptoms during Days 1-13 using:

*Positive and Negative Syndrome Scale (PANSS)* (Chapman et al., 1980): A clinician-rated general assessment measure used to measure psychosis (positive symptoms), emotional or motivational deficits (negative symptoms), and thought disorder.

*Clinician-Administered Dissociative States Scale (CADSS)* (Bremner et al., 1998): A 19 item self-report questionnaire with eight observer ratings designed to assess perceptual, behavioral, and attentional changes that occur during dissociative experiences from NMDA receptor antagonists (Krystal et al., 1994).

h) Intellectual Functioning: In order to obtain an assessment of general intellectual functioning and a reference point for other cognitive assessments, we will complete the two subtest short-form of Block Design and Information from the WAIS-III (Weschler, 1997). This combination correlates at .87 with the Full Scale IQ.

i) Impulsivity and Automatic Motivational Measures: Change from occasional to compulsive drug use may be less dependent on positive reinforcement and more dependent on implicit processes that automatically evaluate the motivational significance of the alcohol cue for affect regulation. Such processes may include “fast” impulsive responses which automatically orient the individual to either approach or avoid the stimulus and “slower,” more reflective processes involving conscious deliberation and emotion regulation. We will assess using impulsive responding using measures which encompass several clinically relevant core components such as rapidity of response, degree of planning, and disregard of future consequences. Additionally, we will also measure implicit alcohol-affect associations as well as individual variations in the ability of incentive stimuli to control behavior. We will evaluate changes in impulsivity and implicit alcohol associations at baseline and then after each medication period. Pavlovian to Instrumental transfer task will be assessed at baseline only.

j) Padua Inventory (Sanavio, 1988): consists of 60 items describing common obsessional and compulsive behavior and allows investigation of the topography of such problems in normal and clinical symptoms.

k) Chronic Stress Scale (CSS) (Turner et al., 1995): This measure is used to assess a person's perception of ongoing and enduring sources of stress in their life conditions. The chronic stress scale (CSS) includes a list of 51 items about common life conditions and situations (e.g., financial issues, work, marriage and relationship, parental, family, social life). The interviewer reads each item aloud and asks the respondent to reply with not true (0), somewhat true (1), or very true (2).

*Self Reports:*

a) *The Behavioral Inhibition System/Behavioral Activation System (BIS/BAS)* (Carver and White, 1994; Gray, 1981) will assess behavioral activation and inhibition, which have been proposed as biological systems underlying behavior and affect. This measure has been shown to have good convergent, discriminant, and predictive validity in which it measures sensitivity rather than the person's typical experience. The BIS will be used to tap the

component of impulsivity related to decreased sensitivity to the negative consequences of behavior.

- b) *Barratt Impulsiveness Scale (BIS)(version 11)* (Patton et al., 1995): This 30 item self-report instrument provides a trait measure of impulsiveness and yields four scores: a total score, nonplanning activity, cognitive impulsivity, and motor impulsivity. Cronbach alpha coefficients range from .79-.83.
- c) *Short Inventory of Problems (SIP)* [153a]: A brief version of the Drinker Inventory of Consequences (DrInC), this is a 15-item test that measures physical, social, intrapersonal, impulsive, and interpersonal consequences of alcohol consumption. Subjects indicate whether each item occurred in the previous 12 months.
- d) *Self Rating of Effects of Alcohol (SRE)* [153b]: This 5-item self-report contains questions related to the number of drinks required for up to four different effects early in the drinking career.
- e) *Alcohol Expectancy Questionnaire (AEQ)* [153d]: This 68-item questionnaire is an empirically derived self-report form designed to measure the degree to which individuals expect alcohol to produce a variety of general and specific positive effects.
- f) *Negative Alcohol Expectancy (NAEQ)* [153e]: This 60-item self-report provides assesses the current level of motivation to restrain/stop drinking and the constituent components of the current level of motivation. The NAEQ also identifies negative expectancies that may serve as a deterrent and represent motivation to stop or restrain drinking.
- g) *Sensation Seeking Scale (SSS)* [153f]: 40-item self report measures individual differences in optimal levels of stimulation and arrival.
- h) *Depression Anxiety Stress Scale (DASS)* [153g]: This 42-item self-report which measures the negative emotional states of depression, anxiety and stress.
- g) *Biphasic Alcohol Effects Scale (BAES)*(Martin et al., 1993): This 14 item self-report, adjective rating scale will be used to measure the stimulant and sedative effects of alcohol during the priming dose on Day 7. This instrument has been found to be sensitive to memantine and naltrexone's effects on alcohol intoxication (pilot date, Kranzler et al., 2000; Reynolds et al., 2004; Swift et al., 1994).
- h) *Childhood Trauma Questionnaire* (Bernstein, et al. 1994): This 28-item self-report inventory that provides brief, reliable, and valid screening for histories of abuse and neglect. It inquires about five types of maltreatment - emotional, physical, and sexual abuse, and emotional and physical neglect. Also included is a 3 item Minimization/Denial scale for detecting false-negative trauma reports.
- i) *Drinking Motives Questionnaire (DMQ)*(Cooper et al. 1992): contains 15 reasons why people might be motivated to drink alcoholic beverages. Participants rate on a 4-point scale how frequently each of the 15 listed reasons motivate them to drink alcoholic beverages. The measure yields three scale scores reflecting different motives for drinking alcohol.
- j) *Brief Self-Control Scale (Tangney et al., 2004)*: provides a rapid brief assessment of self-control and regulation.
- k) *Sensitivity to Punishment and Sensitivity to Reward Questionnaire (SPSRQ)*(Torrubia et al., 2001): consists of 48 yes-no items that included questions about habitual behaviours in response to cues of punishment, frustrative non-reward and novel stimuli as well as stimuli related to reward and approach-related tendencies.
- l) *The Self-Report Habit Index (SRHI)* (Verplanken & Orbell, 2003).: a 12-item index of habit strength developed on the basis of features of habit; that is, a history of repetition, automaticity (lack of control and awareness, efficiency), and expressing identity.
- m) *UPPS Impulsive Behavior Scale* (Whiteside & Lynam, 2003): a 45-item self-report questionnaire which distinguishes four facets of impulsivity: urgency, lack of premeditation,

lack of perseverance, and sensation-seeking. It is scored on a 4-point scale from Strongly Agree to Strongly Disagree.

Laboratory Measures:

- a) *BART* (Lejuez et al., 2002): This is a computerized behavioral task which measures risk-taking propensity by having the subject press a button to inflate a balloon. The more the balloon is inflated, the greater the reward, however, if the balloon pops, the reward is eliminated. The subject must balance potential gain against potential risk of loss.
- b) *Experiential Discounting Task* (EDT) (Reynolds and Schiffbauer, 2004): This delay-discounting task exposes participants to choice consequences during test administration. The EDT involves multiple blocks of choices, one for each delay. Choices are made between a standard amount that is delivered immediately and is certain and a probable amount that is delayed and uncertain. The EDT is sensitive to various levels of alcohol dosing (i.e., between 0 and 0.8g/kg) (Reynolds et al., 2006).
- c) *Alcohol approach-avoidance task* (AAT) (Wiers et al., 2009): We chose to use the AAT to assess automatic alcohol-affect associations since it has been used to show that heavy drinkers with a G allele of the OPRM1 gene have stronger automatic approach tendencies for alcohol. The AAT is an alcohol variety of the Approach Avoidance task developed by Rinck and Becker (2007) and measures approach bias for alcohol related stimuli. The subject pushes or pulls computer presented stimuli according to a content irrelevant feature, the tilt of the stimulus. Pushing the joystick gradually decreases stimulus size, while pulling gradually increases stimulus size. The zooming feature also generates a sense of approach or avoidance (Neumann, 2000). [name] will provide consultation to our group on the AAT.
- d) *The Implicit Association Test (IAT)* (Greenwald et al., 2003): This task measures implicit affective associations with the alcohol. Using a computerized sorting task, individuals simultaneously classify two target conditions, 'alcohol' (ie., wine, beer, pint, vodka, whiskey, wine cooler) versus 'soft drink' (coca cola, juice, orange soda, root beer, sparkling water, 7-up), and two affective categories relevant to drinking, 'pleasant' (ie. talkative, excited, cheerful, happy, funny, lively), versus 'unpleasant' (i.e., nauseous, listless, awful, miserable, sad, annoying). IAT effects will be calculated with the D600 scoring algorithm. Internal consistency for bipolar alcohol-related affective IAT was .79 in (Houben, in press); the bipolar IAT predicted drinking above explicit measures and outperformed five other variants of the IAT(e.g., unipolar positive, unipolar negative IAT).
- e) *A Pavlovian Instrumental Transfer Test (PIT)* will be completed to examine individual variation in the ability of incentive stimuli to control behavior. This task will use a sucrose reinforcer, and so measure PIT as a general tendency and not an alcohol specific tendency. Prior studies have explored the neural mechanisms of PIT with monetary (Talmi et al., 2008) and juice reinforcement (Bray et al., 2008). PIT involves three distinct training phases: (1) a Pavlovian phase, (2) an instrumental learning phase and (3) a transfer phase. Multiple trials occur in each phase.
- g) Ratings of Drinking Behavior During the Alcohol Self-Administration Period: Subjects will be videotaped during the alcohol self-administration portion of the study on Day 6. These videotapes will be rated by two independent raters who will indicate the onset and offset of each sip of alcohol. Using this data, dependent measures will be constructed including time until the first sip and average time to consume each drink.
- h) Blood Alcohol Levels: Blood samples will be drawn to measure plasma levels of blood alcohol (BAC) during the priming dose and during the alcohol self-administration paradigm on day 6. Blood samples will be stored at -4°C and will be analyzed using gas chromatographic techniques at the HRU Laboratory.

